In the study in non-squamous NSCLC, the median OS was 12.2 months among patients in the nivolumab group as compared to 9.4 months among the 290 patients in the docetaxel group; HR 0.72, p=0.002. The 18-month OS rate was 39% with nivolumab vs 12% with docetaxel. Although the progression-free survival (PFS) did not favor nivolumab over docetaxel (median 2.3 months and 4.2 months, respectively), the rate of PFS at 1 year was higher with nivolumab than with docetaxel (19% and 8% respectively). Nivolumab was associated with greater efficacy than docetaxel across all end points in subgroups defined according to pre-specified levels of tumor-membrane expression ( $\geq 1\%$ ,  $\geq 5\%$ , and  $\geq 10\%$ ) of PD-L1. Treatment-related adverse events (TRAEs) of Grade 3 or 4 were reported in 10% of the patients in the nivolumab group (Borghaei, Paz-Ares et al. 2015).

Patients with advanced squamous-cell NSCLC who have disease progression during or after first-line chemotherapy were treated in a Phase 3 randomized study evaluating the efficacy and safety of nivolumab as compared with docetaxel in this patient population ((Brahmer, Reckamp et al. 2015). The OS was 9.2 months with nivolumab vs 6.0 months with docetaxel; HR 0.59,  $p < 0.0001$ . At 1 year, the OS rate was 42% with nivolumab vs 24% with docetaxel. The response rate was 20% with nivolumab vs 9% with docetaxel ( $p = 0.008$ ). The median PFS was 3.5 months with nivolumab vs 2.8 months with docetaxel (HR 0.62,  $p < 0.0001$ ). The expression of the PD-1 ligand was neither prognostic nor predictive of benefit. Treatment-related adverse events of Grade 3 or 4 were reported in 7% of the patients in the nivolumab group as compared with 55% of those in the docetaxel group.

Nivolumab is Food and Drug Administration (FDA)-approved as a single agent for the treatment of patients with metastatic NSCLC with progression on or after platinum-based chemotherapy. Combining AM0010 with nivolumab may present a promising therapeutic combination to address this unmet medical need in patients with advanced NSCLC.

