### **3.2 Number of Patients**

Approximately 50 (25 within each treatment arm). The enrollment will close once approximately 50 patients have been randomized or 31 March 2019.

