## 5.2. Determination of Sample Size

Approximately 50 patients will be randomized to the 2 treatment arms in a 1:1 ratio. With a total of 50 patients, 25 patients each arm would enable evaluating ORR for each treatment arm. With 25 patients in each treatment arm, the 90% confidence interval (CI) for an objective response rate would be (3%, 28%) if 3 patients (12%) had a response; (11%, 42%) if 6 patients (24%) had a response; and (17%, 50%) if 8 patients (32%) had a response.

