**Table JZGD.6.1. Rules for Determining Date of Progression or Censor for Progression-Free Survival (PFS)**

Rule	Situation	Date of Progression or Censor	Outcome
1	No baseline tumor assessments	Date of Randomization	Censored
2	No post baseline assessments and no death	Date of Randomization	Censored
3	No documented progression and no death (with a post-baseline tumor assessment)	Date of last adequate tumor assessment	Censored
4	Patient lost to follow-up (or withdrew consent from study participation) before documented progression or death	Date of last adequate tumor assessment	Censored
5	Progression per scan	Date of documented progression. If a tumor assessment was done on multiple days, use the earliest date for that assessment	Progressed
6	Clinical progression	Date of clinical progression	Progressed
6	Death without documented progression	Date of death	Progressed
7	Documented progression or death after missing $\geq$ two consecutive post-baseline tumor assessments	Date of last adequate tumor assessment before missed assessment or date of randomization, whichever is later	Censored
8	New anti-cancer therapy started without a prior documented progression or death	Date of last adequate tumor assessment before the start of new anti-cancer therapy	Censored
9	Documented progression or death after missing $\geq$ two consecutive post-baseline tumor assessments	Date of last adequate tumor assessment before the start of new anti-cancer therapy	Censored

Note: Progression-free survival and associated outcome is determined by the earliest of the dates above, if more than one situation applies. Two consecutive post-baseline tumor assessments refers to the next 2 protocol scheduled tumor assessments. Time is measured from the last adequate tumor assessment date. The window of the tumor assessment is also considered (that is, the weeks for the scheduled tumor assessments plus the window allowed for each scan is 7 days, for example a patient who goes more than  $(2*7*8+7) = 119$  days is considered missing 2 consecutive assessments) in the first year.

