The PFS curves for each treatment arm will be estimated using the Kaplan-Meier product-limit method. Two-sided, 95% CI for the first quartile, median, and third quartile of PFS will be provided. Progression-free survival rates at fixed time points (every 3 months) will be estimated using Kaplan-Meier estimates on the PFS curve for each randomized arm provided minimum follow-up is longer than time point to generate the rate. Two-sided 95% CIs for the PFS rates will be calculated.

Restricted mean difference in PFS will be calculated. Following the suggestion of Karrison (1997), the restriction time T will be chosen as largest time point t such that the standard error (SE) of the survival estimate at time t in each treatment group is no more than 0.075. For this purpose, we will use the simple, albeit conservative, formula proposed by Peto et al. (1977) for calculating the SE of S(t) as:

$$SE(S(t)) = S(t)\sqrt{1 - S(t)/n(t)}$$

where n(t) is the number of patients still at risk at time t.

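### With 25 patients per arm, the SE-based restriction time puts the restricted mean PFS difference either at about the first scan or in a tail with about one patient at risk; a fixed T should be stated

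*SAP*

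**What the plan says.** SAP 6.5.3.1 plans per-arm Kaplan-Meier curves, quartiles with 95% CIs, and PFS rates every 3 months. It then adds a restricted mean difference between arms. The time limit for that difference comes from the data: "the restriction time T will be chosen as largest time point t such that the standard error (SE" of the survival estimate at t "in each treatment group is no more than 0.075". The SE is a Peto-type formula using the number still at risk. No value, minimum or fallback for T is given.

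For the fixed-time PFS rates the same section sets a different condition: "provided minimum follow-up is longer than time point to generate the rate".

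The sample size was chosen for the response rate: "25 patients each arm would enable evaluating ORR for each treatment arm" (SAP 5.2). It may end up smaller: "The enrollment will close once approximately 50 patients have been randomized or 31 March 2019" (Protocol 3.2). The primary analysis is cut off 6 months after the last patient is randomized (SAP 6.8).

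**The concern.** An SE limit of 0.075 is demanding for 25 patients: a proportion near one half has an SE of 0.10. If the limit fails over the whole middle of the curve, the largest passing time is either very early, before treatment can have separated the arms, or very late, where almost nobody is left.

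SAP 4.2 sets a secondary objective of estimating the combination against nivolumab alone, and this difference is the only between-arm PFS quantity that the SAP names; it lists no hazard ratio and no log-rank test. A value near zero could be read as no PFS benefit when it mainly reflects where T fell. T could also jump between two data cuts, so that their results would not be comparable.

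**Working it through.** **Inputs from the documents.** 25 per arm (SAP 5.2). Limit 0.075 in each arm (SAP 6.5.3.1). First scan at week 8 ± 7 days (Protocol 7.5), so day 63 at the latest. Cut-off 6 months after the last randomization (SAP 6.8). Censoring at the last adequate scan under rule 3 of SAP Table JZGD.6.1: "No documented progression and no death (with a post-baseline tumor assessment". Nivolumab PFS from the non-squamous trial cited in Protocol 1.1: "median 2.3 months and 4.2 months, respectively" (nivolumab first), and "the rate of PFS at 1 year was higher with nivolumab than with docetaxel (19% and 8% respectively". The cited squamous trial has a nivolumab median of 3.5 months.

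**Assumed.** Hazard ratios (HR) 1, 0.6 and 0.4; uniform accrual over 12 months (range 6–18); 20% of events dated exactly and the rest at the next scan (range 0–40%); no dropout. SE = S·sqrt((1−S)/n), the usual Peto form.

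**Plan's own precision figure.** Exact 90% intervals with n = 25 are 3.35–28.2% for 3 responders, 11.0–42.0% for 6 and 17.0–50.4% for 8. They match SAP 5.2.

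**Step 1: when the limit is met.** Without censoring n(t) = 25·S, so SE = sqrt(S(1−S)/25).
- 4 events: sqrt(0.84 × 0.16/25) = 0.0733, passes.
- 5 events: sqrt(0.80 × 0.20/25) = 0.0800, fails.
- By symmetry it passes again only at 21 events (S = 0.16).
- It never binds if n ≥ 0.25/0.075² = 44.4, that is, 45 per arm.
- With 20 per arm the third event already fails: sqrt(0.85 × 0.15/20) = 0.0798.

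**Step 2: ceiling at the early solution.** Both arms must pass, so the faster arm alone can hold T back. With S ≥ 0.84 in both arms up to day 63, the difference cannot exceed 0.16 × 63/30.4375 = 0.33 months.

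**Step 3: the late solution.** With one patient at risk, S·sqrt(1−S) = 0.075 at S = 0.078; with two, the limit is met up to S = 0.113. The rule therefore accepts times that rest on one or two patients.

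**Step 4: where T falls at the primary cut-off.** A Weibull through S(2.3) = 0.5 and S(12) = 0.19 has shape ln(1.661/0.693)/ln(12/2.3) = 0.529 and scale 4.60 months. There were 1000 trials per scenario. Paired percentages count n(t) after / before the drop on an event day.

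| HR | T at or before week 9 | Mean difference in those trials (months) | Mean at T = 5.5 months | True value at 5.5 |
|---|---|---|---|---|
| 1 | 97.5% / 91.5% | 0.00 | −0.04 | 0 |
| 0.6 | 99.8% / 99.2% | 0.03 | 0.60 | 0.84 |
| 0.4 | 99.9% / 99.2% | 0.05 | 1.01 | 1.37 |

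The SD of the early-T estimate is 0.08 and its largest absolute value 0.26. With accrual of 6–18 months (HR 1 and 0.6) the early share is 81–100%. A second simulation used piecewise-exponential curves, medians of 2.3 or 3.5 months and 19% at 1 year. It gave a median T of 6.6–8.0 weeks; in a few settings with median 3.5 and a strong effect the upper end reached 11–15 weeks. With 50 per arm (Weibull, HR 1 or 0.6) no trial had T at or before week 9, and the median T was 7–9 months.

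**Step 5: if 1-year PFS is lower** (primary cut-off, after / before).

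| Curves | At or before week 9 | Beyond 6 months |
|---|---|---|
| Weibull, median 2.3, 10% at 1 year, HR 1 | 71% / 50% | 29% / 49% |
| Weibull, median 2.3, 5% at 1 year, HR 1 | 46% / 25% | 52% / 72% |
| Exponential, both medians 2.3 | 33% / 15% | 65% / 82% |
| Exponential, both medians 3.5 | 78% / 54% | 22% / 46% |
| Exponential, 4.0 vs 2.3 | 80% / 59% | 20% / 40% |
| Exponential, 5.8 vs 3.5 | 93% / 84% | 4% / 12% |

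The exponential curves imply 1-year PFS of 0.5^(12/2.3) = 2.7% and 0.5^(12/3.5) = 9.3%. In the tail a median of one patient is at risk. Across the main Weibull and exponential scenarios with 25 per arm, T fell between week 9 and 6 months in only 0–3.4% of trials.

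**Step 6: a later analysis, 36 months after the last patient** (Weibull of step 4). T is at or before week 9 in 7% / 3% (HR 1), 50% / 31% (HR 0.6) and 93% / 85% (HR 0.4). Nearly all other trials have a median T of 35–37 months, with a median of 1 to 1.5 patients at risk in the smaller arm.

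**The case against.** The best counter-argument is that the location of T depends on one figure. The 19% 1-year PFS comes from non-squamous patients. This trial also enrols squamous disease and excludes a tumor proportion score of 50% or more, the group for which Protocol 1.2.3.1 cites the highest response to anti-PD-1 therapy. A lower 1-year rate is plausible, and step 5 shows that T then often leaves the first scan. This stands. A reader might infer that the difference will be near zero at the primary analysis whatever the drug does. The documents do not support that: the 0.33-month ceiling does not apply when T is in the tail. The tail is no remedy, though, because the estimate then rests on about one patient.

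A reader might also infer that T was left open. It was not: the SAP fixes an algorithm, a threshold and a published source in advance. The fault is narrower, in that the threshold does not suit 25 per arm.

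The SE formula as extracted reads S·sqrt(1−S/n). This may be an artefact of reading the PDF and is not claimed as an error, but the bracket should be checked on the original page. Taken literally it gives 0.98 at baseline with 25 at risk and admits only S of about 0.075, so the middle of the curve is still excluded.

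Finally, the analysis is descriptive (SAP 6.1.1), and readers can compare the arms from the other PFS outputs. That limits the severity without making the planned number useful. Step 6 is also partly inference: SAP 6.8 names no later PFS analysis, although Protocol 3.6 ties study completion to the final analysis of the secondary objectives.

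**Conclusion.** The point holds in a conditional form. That the limit excludes the middle of both curves at 25 per arm is arithmetic, given the usual Peto SE. T then has two likely places.
- **At about the first scan:** over 90% of simulated primary analyses on the protocol's nivolumab figures with 12-month accrual. The average difference there is 0.05 months or less even at HR 0.4.
- **In a tail with about one patient at risk:** common at the primary cut-off if 1-year PFS is nearer 5–10% and the effect is small, and at a later analysis at HR 1 or 0.6. At HR 0.4, T mostly stays at the first scan even then.

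Confidence is high for the exclusion of the middle and moderate for how often each place occurs, because accrual, hazard ratios, share of exactly dated events and 1-year PFS are assumptions. ORR, the Kaplan-Meier quartiles and the 3-monthly rates are unaffected, and no test or error rate is involved. No defect is claimed for OS. The change should be made, but nothing primary depends on it.

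**What to change.** Replace the SE rule in SAP 6.5.3.1 with a fixed T within minimum follow-up, the principle that the section already applies to the PFS rates. One choice is T = 5.5 months (167 days) at the primary analysis: the week-24 scan is due on day 168 and its window closes on day 175, before the cut-off at 6 × 30.4375 = day 183. Keep the same T at any later analysis, and report the difference with its 95% CI. T = 12 months could be added later as supplementary. If the restricted mean is also meant for OS (SAP 6.5.3.2), state a T there too. Because SAP 6.8 allows efficacy summaries at an interim, record that T was chosen from the scan schedule and follow-up, not from the curves.

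The cost is SAP wording only, with the same data and software. The downsides should be stated in the plan:
- **Width.** With mean SE 0.45–0.52, the 95% CI is about ±0.9 to ±1.0 months (1.96 × SE); with 20 per arm about ±1.1. In simulation it excluded zero in about 17–30% of trials at HR 0.6 and 50–68% at HR 0.4, so moderate effects will often not be distinguishable from zero.
- **Attenuation.** Dating progression at scans gives a smaller difference than the underlying progression times: 0.60 against 0.84 months at HR 0.6 (29% less) and 1.01 against 1.37 at HR 0.4 (26% less).
- **Censoring.** About 1–4% of patients are censored before T under rule 3, without dropout.

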#### **6.5.3.2. Overall Survival**

Overall survival is defined as the time from the date of randomization to the date of death due to any cause. Patients who are alive will be censored at the date last known to be alive.

Overall survival will be analyzed in a similar manner as PFS. Duration of follow-up will be summarized.

#### **6.5.3.3. Disease Control Rate**

Disease control rate is defined as the proportion of patients who achieve SD plus CRs and PRs.

Disease control rate will be calculated for each randomized treatment arm and corresponding 95% CI will be provided.

#### **6.5.3.4. Duration of Response**

Duration of response is defined as the time from the date of first documentation of objective tumor response criteria for CR or PR (whichever is first recorded) to the date of the first documentation of tumor progression (clinical progression or progression per scans) or death due to any cause, whichever occurs first. If a patient does not progress following a response, then their duration of response will use the PFS censoring time.

The analysis of response duration will only include ITT patients with CR or PR. Duration of response will be summarized with descriptive statistics (median and 95% CI) for each treatment arm using the Kaplan-Meier method.

Duration of CR is defined as the time from the date of first documentation of objective response criteria for CR to the date of documentation of tumor progression (clinical progression or progression per scans) or death, whichever occurs first.

Duration of SD is defined as the time from randomization until the criteria for progression are met (clinical progression or progression per scans or death, whichever occurs first).

### **6.5.4. Other Efficacy Analyses**

#### **6.5.4.1. Best Objective Response Rate**

Best objective response is calculated based on the overall visit response from each tumor assessment. It is the best response a patient has had following randomization but prior to starting any subsequent cancer therapy, prior to documented progression (clinical progression or

progression per scan) or the last tumor assessment in the absence of documented progression and subsequent cancer therapy.

Best objective response will be summarized using the following response categories: CR, PR, SD, progressive disease, and not evaluable.

#### **6.5.4.2. Time to Response**

Summary statistics of time to objective response will be provided for patients who achieve PR or CR. Time to response is defined as the time from the date of randomization and the date of first documentation of objective tumor response, CR or PR (whichever status is recorded first). No censoring observation will occur by definition.

#### **6.5.4.3. Change in Tumor Burden**

Percentage change from baseline in tumor burden will be calculated at each tumor assessment. Best percentage change from baseline in tumor burden will be calculated as the biggest decrease or the smallest increase in tumor burden from baseline.

Tumor burden is defined as the sum of the longest diameters of the target lesions (the measurable tumor lesions).

The percentage change from baseline in tumor burden is calculated as:

- $(\text{Sum of target lesions at week } x - \text{sum of target lesions at baseline}) / \text{sum of target lesions at baseline} * 100$

### **6.5.5. Sensitivity Analyses**

#### **6.5.5.1. Progression Free Survival**

Progression-Free Survival Sensitivity Analysis 1 (PFS event is disease progression per scan or death): clinical progression will not be considered as a progression event.

Progression-Free Survival Sensitivity Analysis 2: (PFS event is the earlier of disease progression per scan, clinical progression, or death): pseudoprogression without confirmation is not an event (progressive disease).

Progression-Free Survival Sensitivity Analysis 3 (PFS event is the earlier of disease progression per scan, clinical progression, death, or initiation of subsequent anti-cancer therapy): patient initiates subsequent anti-cancer therapy will be considered as a progression event at the date of initiation of subsequent anti-cancer therapy – 1 day.

#### **6.5.5.2. Overall Survival**

Overall Survival Sensitivity Analysis: Patients who crossover will be censored on the first dose date of crossover – 1 day.

## 6.6. Safety Analysis

### 6.6.1. Study Treatments

#### 6.6.1.1. Extent of Exposure

Extent of exposure will be summarized, variables include: duration of treatment, number of cycles, total dose administered, dose intensity, and relative dose intensity for the entire treatment duration as well as for cycles if appropriate. Relative dose intensity (%) will be summarized using the following categories: <50%; 50% to <80%, 80% to <100%, ≥100%. Number and percentage of patients experiencing dose modification for each treatment arm and reasons will be provided.

The key parameters used to calculate dosing are shown in [Table JZGD.6.2](#).

**Table JZGD.6.2. Study Treatment Administration: Definition of Parameters**

	AM0010	Nivolumab
Dosing schedule per protocol	0.8 mg for ≤80 kg body weight 1.6 mg for >80 kg body weight Daily dosing	240 mg Q2W or 480 mg Q4W
Duration of treatment (months)	(last dose date – first dose date + 1) / 30.4375	
Number of Cycles	see cycle definition for Nivolumab	When nivolumab administered If on Q2W schedule, every two doses count as a cycle If on Q4W schedule, every dose is a cycle
Cumulative Dose (mg)	Sum of the actual doses administered to a patient during the treatment period (not including cross over period)	Sum of the actual doses administered to a patient during the treatment period (not including cross over period).
Dose Intensity	mg received in a week (mg/week) cumulative dose / (duration of treatment / 7)	mg received in a cycle (mg/cycle) cumulative dose / total number of cycles
Relative Dose Intensity (%)	Actual dose intensity / planned dose intensity	

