AM0010 in combination with nivolumab has substantial clinical efficacy in the Phase 1b expansion phase in second-line or greater metastatic NSCLC. Nivolumab is one of several agents that are approved for use upon progression from platinum doublet first-line therapy of NSCLC based on improvements in OS when compared to docetaxel. It is the preferred treatment in the second-line setting and has become the benchmark comparator. Nivolumab was also chosen in this study because its activity vs that of the AM0010 combination with nivolumab will show the contribution of components in this treatment setting.

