#### 6.6.1.2.2. Nivolumab

Nivolumab dose reductions are not permitted. A dose will be considered as actually delayed if the delay is exceeding 2 days (i.e.,  $\geq 3$  days from scheduled dosing date). Number of dose delays per patient, length of delay, and reason for delay will be summarized.

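### Nivolumab relative dose intensity cannot register delayed or omitted doses, because SAP Table JZGD.6.2 counts cycles from doses given; odd Q2W counts and the crossover cut-off also need a stated rule

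*SAP*

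**What the plan says.** SAP Table JZGD.6.2 sets the nivolumab schedule as "240 mg Q2W or 480 mg Q4W" and counts cycles as follows: "If on Q2W schedule, every two doses count as a cycle If on Q4W schedule, every dose is a cycle". Dose intensity is "mg received in a cycle (mg/cycle) cumulative dose / total number of cycles", and relative dose intensity is "Actual dose intensity / planned dose intensity". The planned intensity is not given as a number. SAP 6.6.1.1 reports RDI in four bands, from below 50% to 100% or more.

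Cumulative dose is "Sum of the actual doses administered to a patient during the treatment period (not including cross over period"). The rows for number of cycles and duration of treatment carry no such qualifier.

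SAP 6.6.1.2.2 states "Nivolumab dose reductions are not permitted". It then plans a summary of the number, length and reason of nivolumab delays, counting a dose as delayed from 3 days after its scheduled date.

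The protocol treats a cycle as calendar time. Section 6.3 and Appendix A both make it 4 weeks, whether nivolumab is given Q2W or Q4W. Section 6.4.1 allows nivolumab to be delayed for toxicity and for logistic or personal reasons. Section 10.5.5 lists RDI among the exposure variables.

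**The concern.** RDI is meant to show how much of the planned drug was delivered over the time on treatment. Here the denominator grows only when a dose is given, so time without a dose never enters. The bands below 100% therefore cannot show exposure lost to delay or omission. The same table puts AM0010 on a time basis (mg per week over duration of treatment), so only the drug common to both arms is insensitive to delay.

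Protocol 1.3 says of nivolumab that "its activity vs that of the AM0010 combination with nivolumab will show the contribution of components in this treatment setting", and tolerability is a secondary objective. A reader of either result will want to know whether adding AM0010 reduced nivolumab delivery in Arm 1. An RDI table near 100% in both arms would look like an answer without being one.

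Two gaps in the same table add to this. Nothing says how an unpaired Q2W dose is counted, and the crossover exclusion is written for one term of the ratio only.

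**Working it through.** The documents give no RDI value to reproduce, so the table's rules are applied directly.

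**Inputs.** Doses of 240 mg (Q2W) or 480 mg (Q4W), the cycle rule and the ratio "cumulative dose / total number of cycles" come from SAP Table JZGD.6.2. The absence of dose reductions comes from SAP 6.6.1.2.2, and the 4-week cycle from Protocol 6.3. Planned intensity follows as 2 × 240 = 480, or 1 × 480 = 480, mg per 4 weeks.

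**1. The SAP rule with n full doses**
- Q4W: 480n / n = 480 mg/cycle; 480/480 = 100% for any n.
- Q2W, n even: 240n / (n/2) = 480 mg/cycle = 100%.

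No date appears in either expression.

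**2. One delayed dose.** Q4W doses on days 1, 29 and 113; the third was due on day 57, so it is 8 weeks late.
- SAP rule: 1440/3 = 480 = 100%.
- Calendar time: (113 − 1 + 28)/28 = 5 four-week periods; 1440/5 = 288 mg; 288/480 = 60%.

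**3. Range over an assumed 24 weeks on treatment** (6 periods, 6 × 480 = 2880 mg planned)

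| Doses given | Calendar RDI | SAP RDI |
|---|---|---|
| Q4W: 6 / 5 / 4 / 3 | 100 / 83.3 / 66.7 / 50.0% | 100% each |
| Q2W: 12 / 10 / 8 / 6 | 100 / 83.3 / 66.7 / 50.0% | 100% each |

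Four Q4W doses, each 12 weeks after the last, span 3 × 12 + 4 = 40 weeks, or 10 periods. Calendar RDI is 1920/4800 = 40%; the SAP rule gives 100%.

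**4. Odd Q2W count.** Three doses = 720 mg.
- Half cycles allowed: 720/1.5 = 480 = 100%.
- Rounded down: 720/1 = 720 = 150%.
- Rounded up: 720/2 = 360 = 75%.

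A single Q2W dose rounded down divides by zero.

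**5. Incomplete infusion.** One of four Q4W doses half given: (3 × 480 + 240)/4 = 420; 420/480 = 87.5%. The measure can fall for this reason, but not because of delay.

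**6. Crossover, only if post-crossover cycles were counted.** An Arm 2 patient with 3 on-time cycles before and 3 after crossover: 1440/6 = 240 mg/cycle = 50%. With the exclusion applied to both terms: 1440/3 = 480 = 100%.

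**7. Check of the calendar formula on on-time dosing.** Q2W on days 1, 15 and 29: (28 + 14)/28 = 1.5; 720/1.5 = 480 = 100%. Q2W on days 1 and 15, then Q4W from day 29: (28 + 28)/28 = 2; 960/2 = 480 = 100%. Neither an odd count nor a schedule switch distorts it.

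**The case against.** The strongest reply is that delay information is already planned. SAP 6.6.1.2.2 summarises how many nivolumab doses were delayed, for how long and why, and SAP 6.6.1.1 adds total dose and dose modifications with reasons by arm. The 8-week delay in step 2 would appear there. This stands. A reader might infer that a nivolumab shortfall in Arm 1 would go unseen, and the documents do not support that. What remains is that the delay summary does not mention omitted doses, is not expressed as a share of planned exposure, and leaves an RDI table that contradicts it.

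A reader might also infer that RDI is 100% whatever happens. It is not: steps 4 and 5 show odd Q2W counts and incomplete infusions moving it. The exact statement is that delays and omissions cannot lower it when full doses are given.

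Nor do the documents say that crossover is removed from the numerator alone. The cycles row is silent, and SAP 6.7.4 cuts Arm 2 off at crossover for adverse events, which points towards the same cut-off for exposure. The 50% in step 6 is therefore conditional, and the point is an ambiguity to close. Duration of treatment does not enter nivolumab RDI at all; left unqualified, it could only lengthen the treatment duration reported for Arm 2.

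Finally, all analyses are descriptive, with about 25 patients per arm, and no efficacy endpoint uses RDI. That limits the consequence but does not make the ratio informative.

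**Conclusion.** The point holds, within limits. As defined, nivolumab RDI cannot register delayed or omitted doses: it is 100% for any Q4W count and any even Q2W count of full doses, where calendar time gives 60% in the single-delay example and 40% to 83.3% in the other delayed or omitted-dose schedules shown. Three Q2W doses score anywhere from 75% to 150% for want of a counting rule. The crossover exclusion is stated for cumulative dose only; if post-crossover cycles were counted, RDI for Arm 2 crossover patients would be falsely low.

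The damage is one misleading descriptive exposure measure, partly offset by the separate delay summary. ORR, PFS and OS are unaffected. It should be corrected because a stated rule gives a wrong result and the remedy is cheap.

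The conclusion assumes a planned intensity of 480 mg per 4 weeks, derived from the documents' schedule. The dose dates, the 24- and 40-week spans and the crossover split are illustrations, not predictions for this trial.

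**What to change.** In SAP Table JZGD.6.2:

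- Define nivolumab dose intensity as cumulative dose / [(last dose date − first dose date + 14 or 28 days, by the schedule of the last dose) / 28], in mg per 4 weeks.
- State planned intensity as 480 mg per 4 weeks.
- If number of cycles is still reported, say how an unpaired Q2W dose is counted; it would no longer affect intensity.
- Apply the same crossover cut-off to cumulative dose, number of cycles and duration of treatment, ending Arm 2's period at the last nivolumab dose before the first crossover dose. Report the crossover period separately.

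One limit should be noted beside the table: a hold after the last dose that ends in discontinuation is still not captured, and must be read from the delay and discontinuation summaries.

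The cost is table wording and slightly more programming. The delay summary already needs the dose dates. Reported nivolumab RDI will look less favourable than a near-constant 100%. No dosing rule changes.
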